8.1.1. Analyses for Continuous Data

Continuous data will be summarized using descriptive statistics. The following will be presented: number of subjects, arithmetic mean, standard deviation, median, minimum, and maximum.

8.1.2. Analyses for Categorical and Binary Data

Categorical and binary data will be presented using cell counts and percentages for each category. For summaries of change from baseline, the tables will be presented as a cross tabulation with baseline visit along the side and results of each visit along the top.

8.2. Statistical Analyses

8.2.1. Analysis of Efficacy Data

For the following efficacy analyses, data will be summarized for the total of treatment groups, each cohort and each treatment group of Study A0221047, using the merged data of Study A0221047 and Study A0221109. *Subgroup analyses will be conducted that exclude oxybutynin treatment group in cohort 1 of A0221047 from the total for all efficacy endpoints if any subjects who were randomized to oxybutynin group in A0221047 are in FAS.*

All efficacy endpoints of continuous data and their change from baseline will be summarized descriptively by each visit according to 8.1.1.

The presence of IDC will be summarized by each visit according to 8.1.2.

Listing tables will be provided at each timepoint from baseline visit of A0221047 to final visit of this study for all efficacy endpoints of observed values and changes from baseline with

subjects information (ie., subject ID, gender, age, body weight at baseline of A0221047, cohort of A0221047, randomized treatment group in A0221047 and treatment history from the A0221047 start to the end of this study).

8.2.2. Analysis of Safety Data

Tables and listings of safety and demographic data, including adverse events and medical history will be reported in accordance with current Pfizer standards using baseline information at start of A0221047.

Treatment emergent adverse events will be summarized for the total of treatment groups, each cohort and each treatment group of Study A0221047, using the merged data of Study A0221047 and Study A0221109. Treatment emergent adverse events (PT; preferred term) will be also summarized by the period of the onset time from the start of the fesoterodine treatment (0 – 12 weeks (1-84 days), 13 – 24 weeks (85-168 days), 25 – 36 weeks (169-252 days), in or after 37 weeks (\geq 253 days)).

For the following safety analyses, data will be summarized for each treatment group at baseline of Study A0221109, using the data of Study A0221109 alone.

Vital Signs

Blood pressure and pulse rate and their change from baseline will be summarized descriptively for each treatment group, by each visit according to 8.1.1.

Listings of all vital signs will also be created.

Visual Acuity and Accommodation

Visual acuity (LogMAR units) and accommodation (the distance for each eye at which vision becomes blurred – the mean of triplicate measurements) and their change from baseline will be summarized descriptively for each label, by each visit according to 8.1.1.

Listings of visual acuity and accommodation will also be created.

For Visual Acuity, LogMAR units will be derived from the Snellen ratios recorded on the CRF, as shown in the table below. The decimal is the Snellen ratio (whether it is recorded in metres or feet) expressed as a decimal and $\text{LogMAR} = \text{Log}_{10}(1/\text{decimal})$ (recorded to 1 d.p.). Due to the limited space available in the CRF, the Snellen ratio '20/12.5' will be recorded as '20/13', however this should still be converted to a decimal value of 1.60 and a LogMAR value of -0.2 as shown in the table below. If the Snellen Visual Acuity has been recorded in any other format than those shown below, the appropriate conversion to decimal will be determined prior to database lock.

Table 3
Equivalent visual acuity measurements

Snellen visual acuity					
20 ft	6 m	4 m	Decimal	MAR ^a	LogMAR
20/640	6/192	4/128	0.03	32	1.5
20/500	6/152	4/100	0.04	25	1.4
20/400	6/120	4/80	0.05	20.0	1.3
20/320	6/96	4/63	0.063	16	1.2
20/250	6/76	4/50	0.08	12.5	1.1
20/200	6/60	4/40	0.10	10.0	1.0
20/160	6/48	4/32	0.125	8.0	0.9
20/125	6/38	4/25	0.16	6.3	0.8
20/100	6/30	4/20	0.20	5.0	0.7
20/80	6/24	4/16	0.25	4.0	0.6
20/63	6/20	4/12.6	0.32	3.2	0.5
20/50	6/15	4/10	0.40	2.5	0.4
20/40	6/12	4/8	0.50	2.0	0.3
20/32	6/10	4/6.4	0.63	1.6	0.2
20/25	6/7.5	4/5	0.80	1.25	0.1
20/20	6/6	4/4	1.0	1.0	0
20/16	6/5	4/3.2	1.25	0.8	- 0.1
20/12.5	6/3.75	4/2.5	1.60	0.63	- 0.2
20/10	6/3	4/2	2.0	0.5	- 0.3

Snellen Visual Acuity in meters and feet, decimal notation, MAR, and logMAR.

ETDRS charts are based on linear LogMAR score.

^a MAR, minimal angle of resolution (minute of arc).

PVR

PVR and their change from baseline will be summarized descriptively for each label, by each visit according to 8.1.1.

Listings of PVR will also be created.

Clinical Laboratory Evaluation

The incidence of laboratory abnormalities observed at any time during the study will be tabulated following PDS and summary statistics for changes from baseline will be provided by each visit.

Listings of clinical laboratory evaluation will also be created.

CBCL

CBCL(Domain T Scores and Total Scores as captured in the CRF) and their change from baseline will be summarized descriptively for each label, by each visit according to 8.1.1.

Listings of CBCL will also be created.

GPT

GPT (Time to completion, Number of pegs dropped and Number of pegs correctly placed – by dominant/non-dominant hand and whether the 10-peg or 25-peg test was used, separately) and their change from baseline will be summarized descriptively for each label, by each visit according to [8.1.1](#).

Listings of GPT will also be created.

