Assess Study Medication compliance	X ^a		X			X	

a. The Week 0 visit of Study A0221109 is the same visit as Week 24 visit of Study A0221047. All procedures done at Week 24 visit of Study A0221047 will be used as the Week 0 data for Study A0221109. These procedures (Study A0221047 procedures) will not be repeated at Week 0 of Study A0221109.

b. Or in the event of the subject withdrawing early from the study. Urodynamic assessment should only be performed in subjects who have not missed any doses in the 3 days prior to the visit.

c. Telephone calls may be substituted by a clinic visit at the discretion of the investigator.

d. If vital signs or physical examinations show a clinically relevant change from baseline of the precedent Study A0221047, then safety monitoring will occur at a minimum of monthly intervals, or more frequently as clinically appropriate, until the abnormality resolves.

e. PVR only in subjects who are not performing intermittent catheterization or in any subjects who have >1 urinary tract infection (UTI) during the study.

f. Laboratory assessments may be repeated as needed to follow-up on significant findings.

g. Urinalysis: Urine microscopy, culture, and sensitivity to be performed in the event of the presence of symptoms (eg, fever, flank pain), positive leucocytes and/or nitrites on urinalysis, or if the subject has a documented history of vesicoureteral reflux (VUR).

h. Only for female subjects of child-bearing potential. Pregnancy tests may also be repeated as per request of Institutional Review Board (IRB)/Ethics Committee (EC) or if required by local regulations.

i. The bladder diary will be completed for 3 days prior to Final Visit.

j. The dosing log will be completed on a daily basis.

k. At Final Visit, the time of last dose should be recorded.

l. Follow up visit will be done at 4 weeks after Final Visit.

Table 2. Subjects who were randomized to Oxybutynin arm in Study A0221047

Visit	Visit 1	Visit 2	Visit 3	Visit 4	Visit 5	Visit 6	Visit 7	Final Visit ^b	Follow-Up Visit ^l
Week (Weeks from baseline of the precedent Study A0221047)	Week 0 (24)	Week 6 (30)	Week 12 (36)	Week 18 (42)	Week 24 (48)	Week 28 (52)	Week 34 (58)	Week 40 (64)	Week 44 (68)
Allowance (weeks)	-	±2	±2	±2	±2	±2	±2	±2	+2
Clinic visit/Phone call	Clinic visit	Phone call ^c	Clinic visit	Phone call ^c	Phone call ^c	Clinic visit	Phone call ^c	Clinic visit	Phone call ^c
Informed Consent & Assent	X								
Demography	X								

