3. STUDY DESIGN

This is a Phase 3, multi-center, open-label long-term extension study in Japanese NDO subjects who participated and completed in the precedent Study A0221047 which is a 24 weeks, randomized, open label study, to investigate the safety and tolerability of fesoterodine.

This study consists of a 28-week open-label treatment period followed by a 4-week follow-up. In addition, subject in the oxybutynin arm of the precedent Study A0221047 will continue the fesoterodine treatment until Week 40 visit in this study, in order to obtain fesoterodine 1 year treatment data (Figure 1 and Figure 2).

Target number of subjects is not determined because this is the safety extension study but approximately 9 subjects are expected to become eligible for the study.

[figure not shown]
Figure 1. Study Design (Subjects who were randomized to Fesoterodine arms in Study A0221047)

() weeks from baseline of Study A0221047

* Week 0 visit is the same visit as Week 24 visit of Study A0221047.

Figure 2. Study Design (Subjects who were randomized to Oxybutynin arm in Study A0221047)

() weeks from baseline of Study A0221047

* Week 0 visit is the same visit as Week 24 visit of Study A0221047.

As a rule, all subjects should continue to receive the allocated dose in Study A0221047 until the end of the trial, unless a safety/toleration problem occurs. But, only if the investigator judges that the continued treatment with low dose (4 mg/day for subjects >25 kg or 2 mg/day for subjects ≤25 kg) is useful to the subject although the high dose (8 mg/day for subjects >25 kg or 4 mg/day for subjects ≤25 kg) is likely to cause some problems with tolerability, and the subject wants the treatment with the low dose, the dosage may be reduced to the low dose at each clinic visits. Dose should not be increased to the high dose.

Subjects >25 kg who cannot swallow tablets are not permitted to take the BIC formulation and are excluded from the study.

Even if the body weight of subjects with ≤25 kg at baseline of the precedent Study A0221047 increase >25 kg during Study A0221047 or this study, they should maintain the same dose and formulation.

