8.2. Reporting Period

For SAEs, the active reporting period to Pfizer or its designated representative begins from the time that the subject provides informed consent, which is obtained prior to the subject's participation in the study, ie, prior to undergoing any study-related procedure and/or receiving investigational product, through and including 28 calendar days after the last administration of the investigational product. SAEs occurring to a subject after the active reporting period has ended should be reported to the sponsor if the investigator

becomes aware of them; at a minimum, all SAEs that the investigator believes have at least a reasonable possibility of being related to study drug are to be reported to the sponsor.

AEs (serious and nonserious) should be recorded on the CRF from the time the subject has taken at least 1 dose of study treatment through the last subject visit.

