9.3. Safety Analysis

The Safety Analysis Set will be defined as all randomized subjects who have received at least one dose of study medication in this study.

Results from the safety assessments and any AEs will be presented in tabular and/or graphical format adhering to current [Pfizer Data Standards](#). These presentations will be

split by treatment group at baseline in this study. In addition, AE tables during the period from A0221047 study start to end of this study will be produced by cohort and randomized treatment group in A0221047 (including overall summary of safety analysis set in this study). Safety endpoints such as vital signs, laboratory evaluations, weight, PVR, vision testing and CBCL/GPT results will be presented descriptively by treatment group at baseline in this study. Adverse event incidence rates will be provided descriptively.

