6.2.1. Adverse Events

Adverse event information will be collected for all subjects. Information that will be collected includes: nature of event, whether event was serious; date of onset; date of cessation or event continuing; severity of event; relationship of event to study drug; action taken regarding study drug due to the event; clinical outcome of event.

Any events occurring following the start of study drug of fesoterodine or increasing in severity will be counted as treatment emergent. Events that occur in the oxybutynin-treatment period in Cohort 1 of Study A0221047 will NOT be attributed to fesoterodine, unless they started in the oxybutynin-treatment period in Cohort 1 of Study A0221047 and became more severe in the fesoterodine-treatment period.

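### The adverse-event onset table sets three 84-day on-drug periods beside an open last period of 140-154 days that includes off-drug follow-up, so its columns are not comparable as planned

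*SAP*

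**What the plan says.** SAP 8.2.2 plans TEAEs by preferred term on the merged data of A0221047 and A0221109. Besides the overall summary, they "will be also summarized by the period of the onset time from the start of the fesoterodine treatment". The periods are days 1-84, days 85-168, and then "weeks (169-252 days), in or after 37 weeks", the last starting at day 253 with no upper limit.

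Four other provisions decide what enters that last period:

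- SAP 6.2.1: "Any events occurring following the start of study drug of fesoterodine or increasing in severity will be counted as treatment emergent". No end is given.
- Protocol 8.2: events go on the CRF from the time "the subject has taken at least 1 dose of study treatment through the last subject visit".
- Protocol Schedule of Activities, Table 1, footnote l: "Follow up visit will be done at 4 weeks after Final Visit". The allowance is +2 weeks, and adverse events are reviewed at that contact.
- Protocol 3: former oxybutynin subjects "will continue the fesoterodine treatment until Week 40 visit in this study, in order to obtain fesoterodine 1 year treatment data".

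On output, SAP 8.1.2 says "Categorical and binary data will be presented using cell counts and percentages for each category" and Protocol 9.3 says "Adverse event incidence rates will be provided descriptively". Neither document states a number at risk, exposure time or on-drug restriction for each onset period. Neither says whether a child with repeated onsets of a term is counted in each period or only once.

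**The concern.** The primary objective is safety and tolerability in long-term treatment, and this is the only TEAE summary that the SAP describes by time on fesoterodine. A reader will naturally look across its columns to see whether events become more or less frequent with duration. The columns differ in length, and the last mixes time on drug with time after stopping. A difference between columns can therefore come from the layout alone. In event counts, a real fall in rate can also be hidden: a drop of 40% (1 - 84/140) to 45% (1 - 84/154) would show as no change.

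Early stoppers raise a separate problem of classification. Take a fesoterodine-arm child who stops at the Week 12 visit of A0221109, which is Week 36 from A0221047 baseline, or day 252. Follow-up then runs over about days 253-280. An event in that time is tabulated as onset in or after week 37 of fesoterodine, although the child took none in that period. After other stopping dates, off-drug events fall in whichever column follows the last dose.

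**Working it through.** **The plan's boundaries.** 12 × 7 = 84, 24 × 7 = 168 and 36 × 7 = 252, so the stated day limits match their week labels and each closed period is 84 days.

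**Length of the last period, fesoterodine arms.** 24 weeks in A0221047 plus 28 weeks here make 52 weeks, or 364 days on drug.

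- On drug: 364 - 252 = 112 days.
- Follow-up: 28 days, or 42 with the +14-day allowance.
- Total: 112 + 28 = 140 to 112 + 42 = 154 days.
- With the Final Visit allowance of ±14 days: 98 + 28 = 126 to 126 + 42 = 168 days.

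**Ratio to an 84-day period.** 140/84 = 1.67 and 154/84 = 1.83; with the Final Visit allowance, 126/84 = 1.5 to 168/84 = 2.0. On-drug days only: 112/84 = 1.33. The off-drug share is 28/140 = 20% to 42/154 = 27%.

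**Expected event counts at a constant rate.** These follow the lengths. The last column holds 140/392 = 36% to 154/406 = 38% of all events, and each earlier one about 21% (84/392 or 84/406). If the off-drug rate is a fraction f of the on-drug rate, the ratio with 28 days of follow-up is (112 + 28f)/84: 1.33 at f = 0, 1.50 at f = 0.5 and 1.67 at f = 1.

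**Children with an event.** Assume nine completers and a constant rate r per child-year for one term, on and off drug; the documents give no such rate, so a range is shown. If children are counted anew in each period, the expected number is 9 × (1 - exp(-r × days/365)). If each child is counted once, at first onset, it is 9 × (exp(-r × start/365) - exp(-r × end/365)), where start and end are the days elapsed at the period's limits.

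| r | Rule | Days 1-84 | 85-168 | 169-252 | 253 on (140-154 days) |
|---|---|---|---|---|---|
| 0.5 | Anew | 0.98 | 0.98 | 0.98 | 1.57-1.71 |
| 0.5 | Once | 0.98 | 0.87 | 0.78 | 1.11-1.21 |
| 1 | Anew | 1.85 | 1.85 | 1.85 | 2.87-3.10 |
| 1 | Once | 1.85 | 1.47 | 1.17 | 1.44-1.55 |
| 2 | Anew | 3.32 | 3.32 | 3.32 | 4.82-5.13 |
| 2 | Once | 3.32 | 2.10 | 1.32 | 1.21-1.29 |

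Counted anew, the last column is always the highest. Counted once, it is the highest only at r = 0.5; at r = 1 it is below the first column, and at r = 2 below all three.

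**Drop-out.** Suppose the 12.5% drop-out that Protocol 9.1 assumes for A0221047 also applied per 24 weeks of the extension (an assumption). Mean observed time in the last period is then about 127 days, a ratio of about 1.5. The excess over 84 days disappears only if about 40% of the last period's time is lost (1 - 84/140).

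**Former oxybutynin arm.** One year of fesoterodine ending at Week 64 implies a start at Week 12 of A0221047 (64 - 52 = 12), and then the same lengths apply. This start is inferred, not stated. If they had started at Week 0 of A0221109, their last period would be 28 + 28 = 56 to 28 + 42 = 70 days.

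**The case against.** A reader might infer that a constant rate must look like a late rise. The documents do not support that, because the direction depends on a counting rule that they leave open, and under first-onset counting the columns can fall. This objection stands and limits the point to non-comparability. It also shows that the counting rule itself needs stating.

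The practical effect is small. About nine children are expected, there are no hypotheses or decision rules, each child gets a narrative, adverse-event listings are planned, and the last column is openly labelled as open-ended. As an illustration, apply the adult constipation incidence in Protocol 1.2 (4-6%) per 84 days. Counting anew gives 0.36-0.54 children in an 84-day column against 0.59-0.97 in the last. That gap of 0.2-0.4 child is within one binomial standard deviation (0.6-0.9). For dry mouth (19-35%) the gap is 1.0-1.8 children. So the effect matters mainly for frequent terms. This stands too.

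The sponsor's reporting standards, cited in SAP 8.2.2 and Protocol 9.3, may set denominators, a post-treatment limit and counting rules. That is possible, but they cannot be seen here and cannot be assumed to resolve it. If they do, the SAP need only name the rule.

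Finally, exposure figures alone would not make the columns fully comparable. Under SAP 5.3 and Protocol 4.1, the Safety Analysis Set holds only children who completed A0221047, so the early columns are conditioned on not having stopped in that study. This is correct and belongs in a note under the table.

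**Conclusion.** The point holds as a modest, optional improvement to one descriptive table. Followed as written, the period limits and the treatment-emergent definition put off-drug events into columns labelled by time from the start of fesoterodine, and give a 52-week completer a last column of 140-154 days against 84 in each earlier one. At a constant rate, event counts, or children counted anew in each period, are higher in the last column; the expected event ratio is 1.67-1.83 if the off-drug rate equals the on-drug rate and 1.33 if no events occur off drug. These figures assume visits on schedule apart from the follow-up allowance, completion of treatment and, for the former oxybutynin arm, a start at Week 12 of A0221047. The fesoterodine-arm result does not depend on that last assumption.

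A reader might also infer that the overall TEAE count is wrong. It is not: counting through follow-up is an acceptable, conservative rule for that summary.

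**What to change.** In SAP 8.2.2:

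- Limit the four onset periods to events with onset on or before the last fesoterodine dose, and put later events in a separate *after last dose* column.
- State that a child is counted in each period in which the term has an onset.
- Print under each column the number of children on fesoterodine at its start and the on-drug child-days. For nine completers these are 9 × 84 = 756 in each of the first three and 9 × 112 = 1008 in the fourth.
- Note that all children in the table completed A0221047, so the early columns exclude anyone who stopped in that study.

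In SAP 6.2.1, state that the overall TEAE count runs through the follow-up contact. If a sponsor standard already covers any of this, name it instead.

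The cost is a few sentences, one column, two footer rows and a note. The time of the last dose is already recorded (Protocol 6.1.5, 6.2.7 and 7.2.10), so no new data are needed. The downside is that residual or withdrawal effects just after the last dose leave the fourth period; they stay visible in the new column and in the overall count.

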8.2.3. Summary of Efficacy Endpoint Analyses

Table 3. Summary of Efficacy Endpoint Analyses

Endpoint	Analysis Set	Assessment	Planned Statistical Method	Missing Data	Objective
Change in maximum cystometric capacity at each visit relative to baseline	FAS	Week 12 Week 52 (for Fesoterodine arm in Study A0221047) Week 64 (for Oxybutynin arm in Study A0221047) Final Visit	Continuous summaries	No imputation	Efficacy following long-term treatment
Change in detrusor pressure at maximum bladder capacity at each visit relative to baseline	FAS	Week 12 Week 52 (for Fesoterodine arm in Study A0221047) Week 64 (for Oxybutynin arm in Study A0221047) Final Visit	Continuous summaries	No imputation	Efficacy following long-term treatment
Presence of IDC	FAS	Week 12 Week 52 (for Fesoterodine arm in Study A0221047) Week 64 (for Oxybutynin arm in Study A0221047) Final Visit	Categorical summaries	No imputation	Efficacy following long-term treatment
Change in bladder volume at first IDC at each visit	FAS	Week 12 Week 52 (for Fesoterodine arm in Study A0221047) Week 64 (for Oxybutynin arm in Study A0221047) Final Visit	Continuous summaries	No imputation	Efficacy following long-term treatment
Change in bladder compliance at each visit relative to baseline	FAS	Week 12 Week 52 (for Fesoterodine arm in Study A0221047) Week 64 (for Oxybutynin arm in Study A0221047) Final Visit	Continuous summaries	No imputation	Efficacy following long-term treatment

Table 3. Summary of Efficacy Endpoint Analyses

Endpoint	Analysis Set	Assessment	Planned Statistical Method	Missing Data	Objective
Change in mean number of micturitions and catheterizations/24 hours at each visit relative to baseline	FAS	Week 12 Week 52 (for Fesoterodine arm in Study A0221047) Week 64 (for Oxybutynin arm in Study A0221047) Final Visit	Continuous summaries	No imputation	Efficacy following long-term treatment
Change in mean number of incontinence episodes/24 hours at each visit relative to the baseline	FAS	Week 12 Week 52 (for Fesoterodine arm in Study A0221047) Week 64 (for Oxybutynin arm in Study A0221047) Final Visit	Continuous summaries	No imputation	Efficacy following long-term treatment
Change in mean number of urgency episodes/24 hours at each visit relative to the baseline	FAS	Week 12 Week 52 (for Fesoterodine arm in Study A0221047) Week 64 (for Oxybutynin arm in Study A0221047) Final Visit	Continuous summaries	No imputation	Efficacy following long-term treatment
Change in mean voided volume per micturition or catheterization at each visit relative to baseline	FAS	Week 12 Week 52 (for Fesoterodine arm in Study A0221047) Week 64 (for Oxybutynin arm in Study A0221047) Final Visit	Continuous summaries	No imputation	Efficacy following long-term treatment

